#### **Exclusion criteria**

- Previous diagnosis of prostate cancer
- Cognitive disabilities unable to understand study information material

# Study size and outcome

#### Phase I

We assume individual randomization and an effect size of a 40-50% increase in csPC detection (4% in the control arm vs. 5.6-6.0% in the experimental arm), a 5% significance level, 80% power, an average sample size per cluster of m=100-150 men, and an intracluster correlation coefficient ( $ICC = Between-cluster\ variance / (Between-cluster\ variance + Within-$ 

cluster variance) of 0.005-0.01. The ICC measures how similar outcomes from individuals within the same cluster are, compared to individuals from different clusters. It thus quantifies the extent to which outcomes "cluster together" within participating sites. Following Rutterford et al. [8], a sample size of 8,000 men then provides in the range of 58-92% power. Specifically, using plausible values of an effect size of 45%, m=100, and an ICC of 0.008 gives 80% power with 8,000 recruited men.

#### Phase II

The sample size is based on a superiority trial design to detect a 20% increase in csPC detection (4% in the control arm vs. 4.8% in the experimental arm). With a 5% significance level, 80% power, and a 1:1 randomized design, the required sample size is 10,856 participants per group (adjusted for 5% dropout), totalling 21,712 participants.

#### Randomization procedure

Recruitment will take place at more than 30 primary care units across Sweden. To participate in the study, primary care units must use Unilabs as their laboratory service provider.

# Phase I

Participating primary care unit will be 1:1 cluster randomized at study start to one of two study arms:

- Control arm: standard of care with PSA-based diagnostics
- Experimental arm: Reflex testing to Stockholm3 if PSA ≥1.5 ng/ml

To ensure balanced allocation between study arms, stratified block randomization is employed with strata defined by:

- Socioeconomic status (CNI, Care Need Index) of the participating site's catchment area (low, medium, high)
- Annual PSA testing volume at the participating site (low, medium, high)

Primary care units are identified and randomly assigned to a study arm using a centralized, computer-generated randomization list. The randomization is performed by an independent statistician who is not involved in the recruitment process.

#### Phase II

Each referral is automatically assigned a referral identity number (RID) by the laboratory consisting of 8 digits. If the sum of numbers in the RID is even, the man is randomized to the control arm, if the sum of numbers in the RID is odd the man is randomized to the experimental arm. Given that RIDs are assigned consecutively by the laboratory for all the analyses in Sweden, the sum of numbers in the RID will be 50% odd and 50% even.

Study participants will be followed up at 2, 4 and 6 years following the recruitment.

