## Phase II design

Phase II will compare the diagnostic test performance of Stockholm3 (as a reflex to PSA  $\geq$  1.5 ng/ml) to using PSA only. Participants will be 1:1 randomized between control arm with PSA and experimental arm with Stockholm3 as reflex to PSA  $\geq$  1.5 ng/ml. For Phase II, we are thus interested in comparing the test characteristics in isolation (i.e. not Stockholm3's effect on operations, e.g. compliance) and we therefore use randomization on an individual level.

This study phase includes delayed unblinding, meaning that both investigators and participants will remain blinded at the time of blood sampling and will only be unblinded upon receiving the test results. Primary care physicians will recruit men they consider eligible for prostate cancer testing, following standard clinical practice. All participants will undergo blood sampling for both PSA and Stockholm3. Randomization will be performed at the laboratory, and only the assigned test will be analyzed. Men with PSA  $\geq$  3 ng/mL (standard of care) or Stockholm3  $\geq$  11 will be required to undergo further evaluation with MRI.

**Primary Care** Laboratory Primary Care Specialist care Analysis of PSA Referral to MRI if Blood Decision Recruitment R Workup  $PSA \ge 3 \text{ ng/ml or}$ sampling on workup Stockholm3 ≥ 11 Sampling of blood for both Eligible and Referral decision consenting is mandated if participants in PSA and  $PSA \ge 3 \text{ ng/ml or i}$ Analysis of Stockholm3 primary care Analysis Stockholm3 ≥ 11 Primary outcome Stockholm3 if PSA ≥ 1.5-# csPC No previous PC na/ml Secondary outcome # MRI, # Biopsies, # cnsPC, # Benign, Compliance

Figure 2: Phase II design overview

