# **Project description, Phase II**

#### Step 1: Recruitment, consent, and blood sampling

Men with no previous prostate cancer diagnosis, eligible for prostate cancer testing according to standard of care and meeting the study inclusion/exclusion criteria, will be offered to participate in the study. The physicians at participating primary care centers will offer the men participating in the study and inform that the patient will be randomized to either a control arm with PSA or an experimental arm with PSA and Stockholm3 done as reflex test if PSA  $\geq$  1.5 ng/ml.

Men that are interested and have read the *Research Participant Information* will sign an informed consent. Men that are not interested to participate in the study will be offered standard of care.

The physician orders "PSA+" from Unilabs' catalog. The analysis code for the test generates orders for two analyses: a standard PSA test and the Stockholm3 test. The research participant proceeds to the sampling unit, where three blood samples are collected: one

serum tube for PSA and two EDTA tubes for Stockholm3. All samples are transported to Unilabs in Solna/Huvudsta.

In parallel, the randomization is conducted in Unilabs' system. Each referral is randomly assigned to either the control arm (PSA diagnostics) or the experimental arm (Stockholm3 diagnostics).

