# Step 5: Statistical analysis

Primary outcomes:

We will use a generalized linear model (GLM) with a log-link function and binomial
distribution test to for differences in detection rates of csPC. Results will be
presented as risk ratios (RRs) or risk differences (RDs) with corresponding confidence
intervals, adjusting for randomization stratification variables. In the event of
convergence issues, a modified Poisson regression model with robust standard errors
will be used as a backup strategy.

Superiority testing will be conducted to assess whether the Stockholm3-based diagnostic pathway detects a significantly higher number of clinically significant prostate cancers (csPC) compared to the standard PSA-based pathway. The null hypothesis ( $H_0$ ) assumes that both diagnostic strategies have equal detection rates,

whereas the alternative hypothesis ( $H_1$ ) assumes that the Stockholm3 pathway results in a higher detection rate. 95% confidence intervals for effect size estimates will be reported.

- Socioeconomic status (CNI, Care Need Index) of the participating site's catchment area (low, medium, high)
- Annual PSA testing volume at the participating site (low, medium, high)

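### Phase II sets the arm by the digit-sum parity of a consecutive, referral-level laboratory number: a quasi-random rule whose concealment the protocol does not secure

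*Protocol*

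**What the plan says.** All references are to the protocol.

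- **Randomization procedure, Phase II.** "Each referral is automatically assigned a referral identity number (RID) by the laboratory consisting of 8 digits". The arm then follows from that number: "If the sum of numbers in the RID is even, the man is randomized to the control arm", and "if the sum of numbers in the RID is odd the man is randomized to the experimental arm". The justification offered is that "RIDs are assigned consecutively by the laboratory for all the analyses in Sweden", from which the protocol concludes that "the sum of numbers in the RID will be 50% odd and 50% even".
- **Project description, Phase II, Step 1.** The same unit appears again: "Each referral is randomly assigned to either the control arm (PSA diagnostics) or the experimental arm (Stockholm3 diagnostics". This step describes consent and the physician's order first, then sampling, with the allocation made in parallel in the laboratory's system.
- **Phase II design.** Randomization is said to be at the individual level and done at the laboratory, and "both investigators and participants will remain blinded at the time of blood sampling". They learn the arm when the result arrives.
- **Randomization procedure, Phase I.** By contrast, units are assigned from a central computer-generated list by an independent statistician.
- **Project description, Phase II, Step 5.** The primary analysis is described as "adjusting for randomization stratification variables", and Care Need Index (CNI) and annual PSA volume are listed.

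**The concern.** Random allocation needs an unpredictable sequence and concealment of the next assignment until the man is irrevocably in the trial. The parity rule does not supply the first and leaves the second to chance.

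1. The arm is a fixed function of an administrative number. Nothing in the procedure is drawn at random.
2. The rule is printed in the protocol, so an RID that is seen is an arm that is known. The promised blinding at sampling then depends on the RID staying out of sight of clinic, phlebotomist and man until the result. The protocol does not say that it does.
3. The number belongs to the referral. A man ordered a second test gets a new number and possibly the other arm. The exclusion criteria do not bar earlier participation.

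Phase II is meant to isolate test performance, and the Background says adjunct tests lack high-quality randomized evidence. A trial that can be classed as quasi-randomized serves that purpose less well. If cancelled orders, re-orders or selective sampling came to depend on the arm, the difference in detection would mix test performance with case mix.

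**Working it through.** **1. The protocol's 50/50 statement.** I computed digit-sum parity for every number from 0 to 9,999,999. A fixed leading digit only swaps the labels. The share with an odd sum is exactly 50.0%, so the statement about the number series is correct. It does not establish randomness: strict alternation of two arms is also 50/50.

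**2. The protocol's sample size.** Inputs from Study size and outcome, Phase II: 4% versus 4.8%, 5% level, 80% power, 5% dropout. Sidedness is not stated; two-sided fits.

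- Unpooled: n = (1.96 + 0.8416)² × (0.04 × 0.96 + 0.048 × 0.952) / 0.008² = 10,313.4 per group. Divided by 0.95, this is about 10,856, the stated figure.
- Pooled: 10,317 per group, or 10,860 after dropout.
- Evaluable men per arm: 10,856 × 0.95 = 10,313.

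**3. The unit of allocation.** Two sections attach the arm to the referral (Randomization procedure, Phase II; Project description, Phase II, Step 1). One attaches it to the individual (Phase II design). Two RIDs of one man, far apart in the series, would differ in parity about half the time. So the two descriptions agree only if each man has one referral or if a further rule says which RID counts.

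**4. What arm-dependent enrolment would do.** Suppose the tests detect equally well (true risk ratio 1), but men in the experimental arm are, by selection, r times as likely to have clinically significant cancer. With p₀ = 0.04, p₁ = 0.04r and n = 10,313 per arm:

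SE = √{[p₀(1 − p₀) + p₁(1 − p₁)] / n}; chance of a false superiority claim = 1 − Φ(1.96 − (p₁ − p₀)/SE).

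| r (assumed) | p₁ − p₀ | SE | (p₁ − p₀)/SE | False claim |
|---|---|---|---|---|
| 1.00 | 0 | 0.00273 | 0 | 2.5% |
| 1.01 | 0.0004 | 0.00274 | 0.146 | 3.5% |
| 1.02 | 0.0008 | 0.00274 | 0.292 | 4.8% |
| 1.05 | 0.0020 | 0.00276 | 0.724 | 10.8% |
| 1.10 | 0.0040 | 0.00279 | 1.432 | 29.9% |

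**5. How much selection each row needs.** Assume a fraction f of control men, at twice the average risk, end up in the experimental arm. Then r = [(1 + 2f)/(1 + f)] / [(1 − 2f)/(1 − f)], or about 1 + 2f.

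- f = 0.5% (about 52 men): r = 1.010
- f = 1% (about 103 men): r = 1.020
- f = 2.4% (about 248 men): r = 1.049

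The documents give no value for f or r.

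**The case against.** The strongest reply is that the described workflow protects allocation in practice. The man consents and the physician orders a single test code before allocation is described. The laboratory issues the number automatically. Every man gives the same three tubes, so sampling does not reveal the arm. The protocol nowhere shows an RID on an order form or tube label before the result. MRI referral above the thresholds is mandated in both arms, which limits what knowledge of the arm can change later. All of this stands. It makes the weakness a missing guarantee.

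Two stronger readings are tempting, and the document supports neither.

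- **That clinics can foresee the next arm because the rule nearly alternates.** Adjacent RIDs do fall in opposite arms 90.9% of the time. But numbering covers all analyses in Sweden, so unrelated referrals fall between trial men. With random (geometric) gaps, an assumption, successive trial men differ in arm about 52.5% of the time at a mean gap of 10 and 50.3% at 100. The 90.9% does not describe the men in the trial and should not be used against it.
- **That allocation has been breached, or that false claims will reach 10% to 30%.** Those rates need a 5% to 10% case-mix shift across the whole trial. Under the double-risk illustration, even 5% means moving about 250 men.

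It can also be said that an analysis rule for men referred twice may sit in the statistical analysis plan, which is not shown. That could settle which result counts. It would not remove the conflict between referral-level and individual-level allocation in the protocol, nor supply a random sequence.

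The adjustment for stratification variables is a separate mismatch. Covariate adjustment is valid under any allocation and says nothing about concealment.

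**Conclusion.** The point holds as a defect of method. Phase II, as written, allocates by a deterministic, published function of a consecutive referral number. That is quasi-random, its concealment depends on an RID visibility that the protocol leaves open, and its unit conflicts with the promised individual-level randomization. The 50/50 argument does not answer this.

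No breach is shown, and the size of any bias cannot be derived from the document. Conditional on an assumed relative case-mix difference of 1% to 10%, the one-direction false-superiority rate runs from about 3.5% to 30%, against 2.5%. This rests on a 4% control rate, 10,313 evaluable men per arm and a two-sided 5% test. The lower end is reached with few men under the double-risk assumption; the upper end needs extensive selection. Once men are allocated, analysis cannot reliably repair the weakness, so the change belongs before Phase II begins.

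**What to change.** Before Phase II starts, amend the Phase II randomization procedure as follows.

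- Replace the parity rule with a concealed, computer-generated random allocation run in the laboratory system. Simple randomization is enough for about 21,700 men. Avoid small blocks by unit: physicians learn each arm with the result, so later assignments in a block could be guessed.
- Allocate once per man, at his first enrolled referral, and keep that arm on any repeat order.
- State that the allocation is released only with the result.
- Reconcile Step 5 of the Phase II project description, and the matching sentence under its secondary outcomes, with the allocation method: either call CNI and PSA volume prespecified covariates for Phase II, or stratify on them.

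The cost is a programming change at the laboratory, whose effort is not documented, and a protocol amendment. The sample size stays at 10,856 per group. The protocol allows Phase I to be published before Phase II starts, so the amendment need not disturb Phase I.

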# Participation in the study and informed consent

Each research participant will, after reading the *Research Participant Information*, sign an informed consent, either on paper or electronically.

# **Data Collection**

		Phase I		Phase II	
Data collected	Sample space	Control	Experiment	Control	Experiment
Age	Integer	Х	Х	Х	Х
Family history of prostate cancer	Yes No Not known		Х	Х	Х
Use of 5-alfa reductase inhibitors	Yes No Not known		Х	Х	Х
Earlier negative biopsy conducted with the last 12 months	Yes No Not known		Х	Х	Х
Date of blood sampling	Date format	Х	Х	Х	Х
Date of test result report	Date format	Х	Х	Х	Х
Stockholm3 Risk Score	Integer [1-99]		Х		Х
PSA value	Float [0-9,999]	Х	Х	Х	Х
Digital Rectal Examination	Positive Negative Not known	Х	Х	Х	Х
MRI conducted*	Yes No	Х	Х	Х	Х
Date of MRI (only if MRI conducted)	Date format	Х	Х	Х	Х
PIRADS (only if MRI conducted)	1 2 3 4 5	Х	Х	х	Х
Prostate volume and other data from MRI report (only if MRI conducted)	Text	Х	Х	Х	Х
Biopsy conducted*	Yes No	Х	Х	Х	х
Date of biopsy (only if biopsy conducted)	Date format	Х	Х	Х	Х
ISUP (only if biopsy conducted)	Benign 1 2 3 4 5	х	Х	х	х
Percentage Gleason Score 4 (only if positive	Percentage	Х	Х	Х	Х

		Phase I		Phase II	
Data collected	Sample space	Control	Experiment	Control	Experiment
biopsy conducted)					
Cancer length (only if positive biopsy conducted)	Float [0-999]	Х	X	X	X
Type of biopsy (only if biopsy conducted)	Text	Х	Х	Х	Х
Type of instrument (only if biopsy conducted)	Text	Х	Х	Х	Х
Date of PAD report (only if biopsy conducted)	Date format	Х	Х	Х	Х

Results of MRI and biopsy will be followed up at 4 months after blood test to allow for lag in radiology/pathology.

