# **Primary endpoint measures**

• Number of csPC, defined as Grade Group ≥ 2

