#### Step 3: Lab analysis

Samples are received at Unilabs in Solna/Huvudsta.

Samples from primary care units are processed for PSA (control arm) or PSA and Stockholm3 if PSA ≥1.5 ng/ml (experimental arm) and the result is reported to the ordering physician.

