## **Step 5: Data collection**

Data will be collected prospectively by medical record analyses to see if the man was referred to MRI and/or prostate biopsy, and if so, the results from these procedures (Grade Group and PIRADS) will be collected. Unilabs will provide a list of all PSA tests at participating primary care units. Data on percentage of Gleason Grade 4, mm cancer, type of biopsy, instrument used will be collected from analyses of pathology reports. Data on type of MRI protocol and MRI instruments will be collected from analysis of radiation reports.

Karolinska Institutet will enter data into a study database and evaluate the results.

MRI and biopsies performed within 4 months from test results delivered to physician will be included in the analysis.

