#### **Step 4: Data collection**

See "Step 4: Data collection, Phase I" above.

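### The protocol starts the 4-month period for MRI and biopsy outcomes from two different dates, so results may be collected before the primary-endpoint window has closed

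*Protocol*

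**What the plan says.** Two places in the protocol set a 4-month period for MRI and biopsy outcomes.

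- **Data Collection**, in the sentence under the table of data items for both phases: "Results of MRI and biopsy will be followed up at 4 months after blood test to allow for lag in radiology/pathology".
- **Project description, Phase I, Step 5: Data collection**: "MRI and biopsies performed within 4 months from test results delivered to physician will be included in the analysis".

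Phase II, Step 4 refers the reader to "Step 4: Data collection, Phase I". In Phase I, data collection is Step 5, so the step number is wrong, but the intended target is clear. The Phase I inclusion rule therefore also governs Phase II. The Data Collection sentence covers Phase II directly, because its table has columns for both arms of both phases.

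The primary endpoint is "Number of csPC, defined as Grade Group ≥ 2", and that text has no time limit. The data table lists the sampling date and the "Date of test result report" as separate items in all four phase-by-arm columns. It also lists the dates of MRI, biopsy and pathology report.

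**The concern.** The endpoint text sets no window, so these two sentences are the only text that determines which biopsy-proven cancers are found and counted. One starts the clock at the blood sample and the other at delivery of the result. A result cannot be delivered before the sample is taken, so the first date always falls before the second window ends.

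The Data Collection sentence also gives its purpose as allowing for radiology and pathology delay. A look at that time cannot serve this purpose for procedures late in the inclusion window: some are not yet done, and others are done but not yet reported. What is at stake is how completely the primary endpoint is ascertained. If the delay between sample and result differs by arm, the completeness could differ by arm as well.

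**Working it through.** **1. The plan's own figures.** The window does not enter either calculation.

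- *Phase II (Study size and outcome).* Inputs are 4% versus 4.8%, 5% significance (two-sided), 80% power and 5% dropout. n = (1.960 + 0.842)² × [0.04 × 0.96 + 0.048 × 0.952] / 0.008² = 7.8489 × 0.084096 / 0.000064 = 10,313.4. Dividing by 0.95 gives 10,856 per group, as stated.
- *Phase I.* Inputs are 4% versus 5.8% (a 45% increase), m = 100, ICC 0.008 and 8,000 men. The design effect is 1 + 99 × 0.008 = 1.792, so the effective n per arm is 4,000 / 1.792 = 2,232. Power = Φ[(Δ − 1.96·SE₀)/SE₁], with SE₀ (pooled) = 0.006462 and SE₁ = 0.006456. This gives Φ[(0.018 − 0.012665)/0.006456] = Φ(0.826) = 79.6%, against the stated 80%.

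Both figures reproduce, and neither has a term for the follow-up window. Settling the window changes neither.

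**2. The two cut-offs side by side.** Let s be the sampling date, t the days from sample to result, p the days from biopsy to pathology report, and take 4 months as 122 days.

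| Event | Date |
|---|---|
| Follow-up under Data Collection | s + 122 |
| Inclusion window opens (Phase I, Step 5) | s + t |
| Inclusion window closes | s + t + 122 |
| Latest report on a qualifying biopsy | s + t + 122 + p |

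The gap between the follow-up date and the close of the window is (s + t + 122) − (s + 122) = t. Qualifying biopsies without a report at the follow-up date are those done from s + 122 − p to s + t + 122, which is the last t + p days of the window.

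**3. Size of the gap.** The protocol gives neither t nor p. For assumed t of 3, 7, 14 and 28 days, t/122 is 2.5%, 5.7%, 11.5% and 23.0%. With assumed t = 7 and p = 14, (t + p)/122 = 21/122 = 17.2%. These are shares of time and not of cancers. Turning them into shares of cancers needs the distribution of time from result to biopsy, which the protocol does not give.

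**4. By arm.** If collection stopped at s + 122, the time for work-up after the result would be 122 − t. The arms would differ by t(experimental) − t(control). Phase I, Step 3 shows that the experimental arm adds a Stockholm3 assay when PSA is at least 1.5 ng/ml, which suggests a longer t. The arms also use different tubes (Blood handling), and no turnaround time is given for either, so the difference cannot be quantified.

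**5. Illustration with assumed losses only.** Suppose 5% of csPC were missed in both arms. The risk ratio would be unchanged, and power would go from 79.6% to 77.4% in Phase I and from 80.0% to 77.8% in Phase II (10,856 × 0.95 = 10,313 per arm). A 5% loss in the experimental arm only would move the risk ratio from 1.45 to 1.38 and from 1.20 to 1.14. A 5% loss in the control arm only would move it to 1.53 and 1.26. Direction and size depend entirely on the assumed losses.

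**The case against.** Only the Step 5 sentence states what is included in the analysis. The Data Collection sentence says when results are followed up and excludes nothing, so the endpoint window is not strictly defined twice. The protocol does not say that records are read only once or that collection ends at 4 months. Step 5 describes prospective review of medical records, and a later contact is planned: "Study participants will be followed up at 2, 4 and 6 years following the recruitment". With all the relevant dates recorded, the Step 5 rule can be applied exactly to any sufficiently late extraction.

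Most of this stands. A reader might infer that late cancers are definitely lost, that the loss falls harder on the experimental arm, and that power drops well below plan. The documents support none of these. Loss requires a single early look, which is not stated. Arm dependence requires turnaround times, which are not given. Any power figure requires loss rates that must be assumed. It is also not stated whether the 4% planning rate is already a 4-month rate, in which case the planning figure would already reflect cases falling outside such a window.

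The objection does not remove the conflict. Recovering late cases depends on an extraction after the window closes, and the protocol schedules none. The next follow-up it names is at 2 years, appears under the Phase II randomization heading, and has no stated content. A SAP not at hand may settle the anchor, but the two protocol sentences would still disagree.

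**Conclusion.** The inconsistency is real and affects ascertainment of the primary endpoint in both phases. Taken literally, the Data Collection time point precedes the close of the Step 5 window by the sample-to-result time and leaves no room for pathology on late biopsies. If results are collected then and not revisited, some csPC that qualify under Step 5 may be missed.

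That is as far as the documents go. The size of any loss cannot be computed, unequal loss by arm is possible but not established, and the stated sample sizes and power are unaffected. The conclusion assumes only that results follow samples and that pathology reporting takes time. The protocol acknowledges both by recording the dates separately. The wording should be settled before outcome data are extracted, particularly since Phase I is unblinded.

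**What to change.** 1. Use one anchor for both phases: the date the result is delivered to the physician, which Phase I, Step 5 already uses. This gives every man the same time for work-up after the result. A sampling-date anchor would let laboratory turnaround shorten that time.
2. Amend the Data Collection sentence so that each man's records are extracted only after his window has closed plus a stated allowance for pathology reporting. The trial team should set the allowance from the reporting times at its sites.
3. State that a csPC counts if the biopsy was performed within the window, whatever the date of the pathology report.
4. Correct the step number in the Phase II cross-reference.

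The cost is protocol wording and a somewhat later extraction. No new data items are needed. The Timeline section should be checked against the change: a man whose result is delivered after February 2026 has a window closing after June 2026, which is when the study is expected to end.
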